#### **5.2 RATIONALE FOR TRIAL DESIGN AND CONTROL GROUP**

A double-blind, placebo-controlled, parallel-group trial design was chosen in accordance with the concepts in ICH E10, Choice of Control Groups and Related Issues in Clinical Trials, in order to provide comparable treatment groups and minimal chance of selection or investigator bias. The trial has a 14-21 day Pretreatment Period to establish a baseline without therapy and to familiarize patients with data collection methodology (ie, eDiary), a 12-week Treatment Period to compare the test treatment to a placebo control, and a 4-week RW Period to determine if a rebound (or worsening of symptoms from baseline) or other withdrawal effects might occur after linaclotide treatment has been withdrawn.

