19. Patient used Rescue Medicine (bisacodyl tablet or suppository) or any other laxative, suppository, or enema, on the day before or the day of the Randomization Visit prior to randomization.

20. Patient reported using a Prohibited Medicine (excluding laxatives, suppositories, and enemas) during the Pretreatment Period or is not willing or able to abide by the restrictions regarding use of Prohibited Medicines defined in [Appendix 2](#). (Note: The use of fiber, bulk laxatives, or stool softeners [such as docusate] is acceptable provided the patient has been on a stable dose during the 30 days before the Screening Visit and plans to continue on a stable dose throughout the trial.)

21. Patient has been hospitalized for a psychiatric condition or has made a suicide attempt during the two years before the Randomization Visit.

22. Patient has taken commercially available linaclootide (LINZESS®) or plecanatide (TRULANCE™) or received an investigational drug during the 30 days before the Screening Visit.

23. Patient has an acute or chronic condition that, in the investigator's opinion, would limit the patient's ability to complete or participate in this clinical trial.

24. Patient has previously entered the Pretreatment Period of this trial.

25. Patient is directly or indirectly involved in the conduct and administration of this trial as an investigator, sub-investigator, study coordinator, other trial staff member, or employee of Ironwood Pharmaceuticals, Forest Laboratories, Actavis, or Allergan; or the patient is a first-degree family member, significant other, or relative residing with one of the above persons involved directly or indirectly in the trial; or the patient is enrolled in this trial at another clinical trial site.

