## **7.7 CONCOMITANT MEDICINES**

A complete list of drugs that are conditionally allowed and drugs that are not allowed as concomitant medicines for either episodic or chronic use or as Rescue Medicine is provided in [Appendix 2](#). During the Pretreatment, Treatment, and RW Periods, patients may use dispensed, protocol-permitted laxatives (bisacodyl tablets or suppositories) as Rescue Medicine when at least 72 hours have passed since their previous BM or when their symptoms become intolerable. In order to qualify for randomization into the Treatment Period, patients must not have used Rescue Medicine on the day before the Randomization Visit or on the day of the Randomization Visit prior to randomization. Patients must agree to refrain from using Rescue Medicine from the time they arrive at the clinic for the Randomization Visit through the day after randomization.

At the Screening Visit, all ongoing medicines or investigational products taken by the patient will be recorded. Past use of certain medications to manage IBS-C symptoms, even if not ongoing at the time of the Screening Visit, will be recorded in the Prior IBS-C Symptom Management Assessment (refer to Section [8.2.6](#) and [Appendix 7](#)) at the Screening Visit.

Any over-the-counter or prescription laxatives, suppositories, or enemas used to treat IBS-C may not be used during the Pretreatment, Treatment, and RW Periods and may not be used on the day before the Pretreatment Visit. Other prohibited medicines may not be used during the Pretreatment, Treatment, and RW Periods and may not be used during the 14 days before the Pretreatment Visit (refer to [Appendix 2](#)). Thereafter, any changes in concomitant medicines or new medicines added will be recorded on the eCRF. Concomitant medicines will be recorded at study visits throughout the entire trial. Rescue Medicine use will be documented by the patient via eDiary.

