Abdominal bloating is measured daily using an 11-point NRS. For each week on treatment, the weekly abdominal bloating score is the mean of the non-missing daily values.

- Percent Change from Baseline in Abdominal Pain at Each Week

Percent change will be calculated as  $100 * \text{the Change from Baseline in Abdominal Pain at Worst at each week divided by the baseline abdominal pain score.}$

- Change from Baseline in Percent of Days with Use of Rescue Medicine over the Treatment Period

The percent of days using per-protocol rescue medicine or any other laxative, suppository, or enema during each week will be calculated as  $100 * \text{the number of days rescue medicine was used during the week divided by the total number of days on treatment.}$

- SBM Within 24 Hours After First Dose Responder

A patient meets the SBM Within 24 Hours After First Dose Responder criteria if the amount of time between the randomization date and time and the time of first reported SBM is less than or equal to 24 hours. For patients who did not take their first dose of study medication on the randomization visit, then the first reported SBM must occur on the same study day as the first dose study day. Randomization date and time is utilized as a surrogate for the date and time of first dose because only first dose date, not time, is captured.

- 6/12 Week Abdominal Pain 30% Responder

A 6/12 Week Abdominal Pain 30% Responder is a patient who meets the Weekly Abdominal Pain 30% Responder criteria for at least 6 out of the 12 weeks of the Treatment Period. For each week in the Treatment Period, a Weekly Abdominal Pain 30% Responder is a patient who has a decrease from baseline of at least 30% in the respective weekly abdominal pain score. If a patient did not enter information into the eDiary on at least 4 days for a particular Treatment Period week, the patient will not be considered a Weekly Abdominal Pain 30% Responder for that week.

- 6/12 Week Abdominal Pain Responder

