#### **7.9.4        *Randomized Withdrawal Period Endpoints***

For the RW Period, statistical analyses will be presented by treatment sequence (treatment sequences defined in Section 7.1.4).

The following endpoints will be calculated for the RW Period following the methods described for the primary and additional endpoints in Sections 7.9.1 and 7.9.3:

- Change from Baseline in Abdominal Score at Each Week
- Change from Baseline in Abdominal Bloating at Each Week
- Change from Baseline in Abdominal Discomfort at Each Week
- Change from Baseline in Abdominal Pain at Each Week
- Change from Baseline in CSBM Frequency Rate at Each Week
- Change from Baseline in SBM Frequency Rate at Each Week
- Change from Baseline in BSFS (Stool Consistency) at Each Week
- Change from Baseline in Stool Consistency at Each Week
- Change from Baseline in Percent of Days with Use of Rescue Medicine over the RW Period

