**Table 9.2-1 Analysis Time Windows for Efficacy Analysis**

Period	Analysis Week	Beginsa	Endsa
Pretreatment (Baseline b )	Week -2	Day -14	Day -8
	Week -1	Day -7	Day 1 (time of randomization)
Treatment	Week 1	Day 1 (time of randomization)	Day 7
	Week 2	Day 8	Day 14
	Week 3	Day 15	Day 21
	Week 4	Day 22	Day 28
	Week 5	Day 29	Day 35
	Week 6	Day 36	Day 42
	Week 7	Day 43	Day 49
	Week 8	Day 50	Day 56
	Week 9	Day 57	Day 63
	Week 10	Day 64	Day 70
	Week 11	Day 71	Day 77
	Week 12	Day 78	Day of last treatment period dose day c (usually Day 85)
RW	Week 1	RW Day 1	RW Day 7
	Week 2	RW Day 8	RW Day 14
	Week 3	RW Day 15	RW Day 21
	Week 4	RW Day 22	Day of last RW dose (usually day 28)

Note: There is no Day 0 or Week 0. For eDiary assessments in which a patient is asked to report if an event occurred “yesterday” or “today” (e.g., a bowel movement or rescue medication use), these windows pertain to when the event occurred, not to when the event is reported. For example, if a patient reports in eDiary on Day 78 a bowel movement occurring “yesterday,” that bowel movement (and subsequent stool consistency and straining scores) would be included in Analysis Week 11, not Analysis Week 12.

- a Relative to the date of randomization or first RW dose; Day 1 = the day of randomization; RW Day 1 = the day of first RW dose. For the calculation of rates (eg, stool frequency rates) in which the duration of a week or the overall period is calculated to the nearest hour, a day begins and ends at midnight.
- b Baseline values for efficacy parameters will be derived from the daily eDiary and eCRF data collected in the Pretreatment Period, specifically the period from 14 days before randomization up to the time of randomization.
- c For patients who fail to provide the date of last dose at the last visit, the later date of the last known dose (drug dispense eCRF) or the last eDiary date will be used to impute the last dose date.

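### The rescue-medicine percentage has a denominator that fits neither a single week nor baseline; once that is repaired, days on which rescue is barred still leave baseline and Week 1 somewhat low

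*SAP*

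**What the plan says.** - **Formula.** SAP 7.9.3: "The percent of days using per-protocol rescue medicine or any other laxative, suppository, or enema during each week will be calculated as" 100 times the rescue days in the week divided by all the patient's days on treatment. The item's title refers to the whole Treatment Period, but the formula is weekly. Protocol 10.4.6 uses the same denominator. Neither document gives a formula for the baseline percentage.
- **Windows.** SAP Table 9.2-1, footnote b, takes baseline from "specifically the period from 14 days before randomization up to the time of randomization". Week 1 runs from randomization on Day 1 to Day 7.
- **Barred days.** Protocol 6.2, criterion 19, excludes a patient who used any laxative, suppository or enema "on the day before or the day of the Randomization Visit prior to randomization". Protocol 7.7 repeats this for rescue medicine: "patients must not have used Rescue Medicine on the day before the Randomization Visit or on the day of the Randomization Visit". It also has patients agree to "refrain from using Rescue Medicine from the time they arrive at the clinic for the Randomization Visit through the day after randomization". Otherwise rescue is open: "During the Pretreatment, Treatment, and RW Periods, patients may use dispensed, protocol-permitted laxatives". No bar is stated around RW Day 1.
- **RW Period.** SAP 7.9.4 lists "Change from Baseline in Percent of Days with Use of Rescue Medicine over the RW Period". Protocol 10.4.9 keeps the pretreatment baseline for RW endpoints. Protocol 5.2 gives the purpose of the period: "to determine if a rebound (or worsening of symptoms from baseline"), or other withdrawal effects, might follow withdrawal. SAP 7.9.4.1 plans descriptive statistics and a 95% CI for each sequence, without inference.
- **Status.** SAP 7.9.3 places this endpoint outside the multiplicity-controlled sequence.

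**The concern.** A percentage of days is only interpretable if numerator and denominator cover the same days. Here the numerator is one week and the denominator, as written, is the whole time on treatment. Baseline has no denominator at all, so the change from baseline is not defined.

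A programmer who repairs this by using days in the window meets a second problem. Rescue use is zero by eligibility on Day -1 and on Day 1 before randomization, and zero by agreement for the rest of Day 1 and on Day 2. These days fall inside the baseline and Week 1 windows. Weeks 2 to 12 and the RW Period contain none. A percentage with built-in zero days is then subtracted from one without them. The place where this matters most is the RW summary, where each sequence is set against its own pretreatment baseline and the period is meant to show any worsening.

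**Working it through.** The documents give no rescue rate and no figure for this endpoint, so there is nothing to reproduce. Let p be the true share of allowed days with rescue use. I assume p = 20% for illustration and show 5% to 40%.

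**1. Formula as written.** For a completer with 84 days on treatment, a patient using rescue every day of a week scores 7/84 = 8.3%. With the 28 RW days as denominator the cap is 7/28 = 25%. At p = 20% a normal week reads 7 × 0.20/84 = 1.7%, or 7 × 0.20/28 = 5.0% in the RW Period. Set against a baseline that someone computes on window days (18.6% or 17.3%, step 2), unchanged habits show -16.9 to -15.7 points in the Treatment Period and -13.6 to -12.3 points in the RW Period. That is a false improvement.

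**2. Denominator corrected to days in the window.** Day -14 to Day -2 gives 13 allowed days.
- Baseline: 13p/14 if the part-day before randomization is not counted, 13p/15 if it is. The relative deficit is 1/14 = 7.1% or 2/15 = 13.3%.
- Week 1: 5p/7, a deficit of up to 2/7 = 28.6%.
- Later weeks and the RW Period: p.

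| p | Baseline (/14, /15) | Later weeks and RW | Spurious change, points |
|---|---|---|---|
| 5% | 4.6%, 4.3% | 5% | +0.4 to +0.7 |
| 10% | 9.3%, 8.7% | 10% | +0.7 to +1.3 |
| 20% | 18.6%, 17.3% | 20% | +1.4 to +2.7 |
| 30% | 27.9%, 26.0% | 30% | +2.1 to +4.0 |
| 40% | 37.1%, 34.7% | 40% | +2.9 to +5.3 |

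At p = 20%, Week 1 reads 14.3%, so unchanged habits show -4.3 to -3.0 points there.

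**3. Between arms.** A true 10-point difference appears as 10 × 5/7 = 7.1 points in Week 1 and 10 × 82/84 = 9.8 over 12 weeks.

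**4. One patient.** At p = 20% the RW shift is 28 × 0.20 × 1/14 = 0.40 to 28 × 0.20 × 2/15 = 0.75 of a rescue day in 28, against a per-patient SD of about 12 to 13 points. The chance that an unchanged patient shows any increase rises from 45% to between 50% and 61%.

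**5. A sequence mean.** Simulation assumptions: 120 patients in 290-Placebo (300 per arm, re-randomized 1:1, 80% completing), patient rates Beta(3m, 3(1-m)) with mean m, independent days, RW rate equal to the pretreatment rate. Share of trials whose 95% CI lies wholly above zero:

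| Mean rate | 15-day baseline | 14-day baseline | Barred days removed |
|---|---|---|---|
| 15% | 61% | 21% | about 2.5% |
| 20% | 76% | 29% | about 2.5% |

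If half of the barred use moves to other days in the window, the figures at 15% and 20% fall to 19% and 26% (15-day) or 9% and 11% (14-day). If all of it moves, they are about 3%.

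**The case against.** The tempting stronger reading is that a patient who resumes pretreatment habits will look like a rebound, so that the RW tables will raise a false alarm. Several points count against it.

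- **Direction.** The weekly formula as written gives the opposite sign (step 1). The upward shift appears only after the denominator is corrected, or if the RW value is taken once for the whole period. This stands, and it makes the denominator the primary issue. One could charitably read the denominator as days on treatment within that week, but the SAP does not say so, and baseline would still have no formula.
- **Size.** The 61% and 76% figures need Day 1 counted as a whole baseline day, independent days and no shifting of use. They are upper bounds. Rescue is taken after 72 hours without a bowel movement or for intolerable symptoms, so uses are likely to be spaced and partly movable. This stands for use brought forward. Use put off until after Day 2 leaves the baseline window and does not restore it, though it can reduce the Week 1 dilution.
- **Cancellation.** 290-Placebo and 290-290 come from the same arm by 1:1 re-randomization and share the same expected baseline deficit, so it drops out when they are compared. Both are reported. In Weeks 2 to 12 it likewise cancels between arms.
- **Inference.** RW results are descriptive and the documents set no rebound threshold. A CI above zero is not a planned test, and eight other RW endpoints cover symptoms and bowel function.
- **Over-correction.** If uses are at least 3 days apart (an assumption), at a true 20% the 13-day baseline reads 20.9%, the 14-day one 19.4% and the 15-day one 18.1%. At 30% the 13-day error is 2.0 points against 0.3 for 14 days. At 10% to 15%, 13 days is closer than 14, and at rates up to 20% it always beats 15. This stands in part and is why a sensitivity summary is needed.
- **Week 1.** Fewer rescue days truly occurred then. The low value is real use under a restriction, so the issue is comparability with other weeks.

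**Conclusion.** The denominator is wrong as written: it is undefined at baseline and compresses weekly values to at most about 8% for a completer. Excluding the barred days is a cheap further improvement. Without it, a corrected formula leaves baseline about 7% to 13% low and Week 1 up to 29% low in relative terms. At an assumed 20% rate, each RW sequence mean then carries about +1.4 to +2.7 points with no change in habits. The shift halves if half of the barred use moves to earlier days in the window and vanishes if all of it does.

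The documents do not support calling this a false rebound for individual patients, where it is negligible, or for the comparison of 290-Placebo with 290-290, where it cancels. It affects one exploratory endpoint and no confirmatory conclusion. The rescue rate, completion rate and day-to-day pattern are all assumptions.

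**What to change.** In SAP 7.9.3 and 7.9.4, state a baseline formula and divide days of use by eligible days in the same window:

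- baseline: Day -14 to Day -2, 13 days;
- Week 1: Day 3 to Day 7, 5 days;
- later weeks and the RW Period: days in that week or period, shortened as in SAP 9.2 for withdrawals.

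Say whether the reported value is weekly, for the whole period, or both. List any use on Days 1 and 2. Show the all-days version as a sensitivity summary, because eligible-day counting can slightly overstate baseline when uses are spaced. Read any worsening in 290-Placebo alongside 290-290. Leave the rescue rules as they are.

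The cost is a short passage of SAP text and a changed day range in one derivation. The endpoint would have a slightly shorter baseline than the other efficacy measures, Week 1 would rest on 5 days, and non-compliant use on Days 1 and 2 would be listed and left out of the main percentage.

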#### **10.4.7 Additional Efficacy Analysis**

Change-from-baseline endpoints and Treatment Satisfaction will be analyzed utilizing the same MMRM methods as described for the primary analysis in Section 10.4.2, and by visit as described in Section 10.4.4. Responder endpoints will be analyzed using the methodology defined in Section 10.4.4.

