### 7.9.1.1 *Analyses of the Primary Endpoint*

Inferential testing between the linaclotide 290 µg and placebo groups with regard to the change from baseline in abdominal score over the Treatment Period will be evaluated employing a mixed model with repeated measures (MMRM) framework with week (categorical), treatment, geographic region, and week-by-treatment fixed effects, patient as the random effect, and baseline value as a covariate. An unstructured covariance structure will be utilized to model the covariance matrix. Descriptive statistics based on the MMRM model will include least-squares (LS) mean change from baseline for each treatment, the LS mean difference between linaclotide 290 µg and placebo, corresponding 95% CIs, and the p-value associated with the comparison.

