### 7.12.1 Irritable Bowel Syndrome–Quality of Life Assessment (IBS-QOL)

The IBS-QOL parameters consist of the overall average score and eight subscale scores (ie, dysphoria, interference with activity, body image, health worry, food avoidance, social reaction, sexual, and relationships). For the Week 12/ETP Visit and the Week 16/EOT Visit, change from baseline in the IBS-QOL overall average score and the subscale scores will be analyzed using an ANCOVA model with fixed effect terms for treatment group and geographic region and the corresponding baseline IBS-QOL score as a covariate.

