For the Treatment Period or RW Period, diary day is calculated as diary date – date of randomization or date of first RW dose + 1. For the Pretreatment Period, diary day is calculated as diary date - date of randomization. However, the day of randomization is always trial Day 1. Patients will complete their diary entries once a day, with the exception of Day 1 of entry into the Treatment Period, during which 2 diary data sets will be collected. On Day 1, daily questions will be entered before and after the randomization, whereas weekly questions will be entered before but not after randomization.

If a patient withdraws during the Treatment Period or RW Period, the patient's Treatment Period or RW Period shall end on the day of the last dose. The affected Treatment Period or RW Period week shall be shortened to the end of the withdrawn patient's Treatment Period or RW Period, and all subsequent Treatment Period or RW Period weeks will be missing for that patient.

**Table 9.2-2** presents the analysis weeks assigned for the efficacy analysis of the patient diary data related to Weekly Questions (e.g., Weekly Patient Assessment of Constipation Severity, Weekly Patient Assessment of IBS Symptom Severity, Weekly Patient and Assessment of Adequate Relief, and Weekly Patient Assessment of Treatment Satisfaction).

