##### ***Gaps in the eDiary Data***

If a patient does not complete either a spontaneous or evening report every day, there will be gaps in the data.

There will be no adjustments for these gaps in the eDiary data for the efficacy data analyses using an OC approach. Effectively, this means that analyses will assume that no rescue medicine use or BMs occurred during these gaps.

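### The weekly rescue-medicine percentage sets one week's days of use against all days on treatment, so its scale depends on each patient's treatment duration and does not match the baseline

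*SAP*

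**What the plan says.** Both documents give the same rule. In SAP Section 7.9.3 and protocol Section 10.4.6, the percent of days with rescue use in each week is 100 times "the number of days rescue medicine was used during the week divided by the total number of days on treatment". Neither limits days on treatment to the week in question, and no entry under SAP Section 8.0 alters the rule.

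The SAP titles the endpoint "Change from Baseline in Percent of Days with Use of Rescue Medicine over the Treatment Period", and Section 7.9.4 carries it into the Randomized Withdrawal (RW) Period under a matching whole-period title. Most neighbouring change-from-baseline endpoints built on diary data are titled by week.

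No separate baseline formula is given. Efficacy baselines come from the Pretreatment Period, "specifically the period from 14 days before randomization up to the time of randomization" (SAP Table 9.2-1, footnote b).

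On the model, protocol Section 10.4.7 is broad: "Change-from-baseline endpoints and Treatment Satisfaction will be analyzed utilizing the same MMRM methods as described for the primary analysis in Section 10.4.2". SAP Section 7.9.3.1 is narrower and gives the MMRM to continuous change-from-baseline endpoints defined at each week. That model contains "week-by-treatment fixed effects, patient as the random effect, and baseline value as a covariate" (SAP Section 7.9.1.1).

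**The concern.** A percent of days needs a numerator and denominator over the same span. Here one covers a week and the other all of treatment. Three things follow if the rule is programmed as written.

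- Weekly levels and between-arm differences come out far too small, by a factor that depends on how long each patient stayed on treatment. Two patients with identical use in the same week get different scores.
- The baseline cannot be computed by the rule, because days on treatment are zero before randomization. Whatever is used instead is on another scale, and the change from baseline loses its meaning.
- The formula says weekly and the SAP title says whole period. These are different endpoints and call for different models, so the programmer must guess.

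At stake are the reported estimates and confidence intervals for rescue use. SAP Section 7.7 sends the summary of per-protocol rescue medicine to Section 7.9.3, so this is the governing definition. In the RW Period the endpoint is descriptive only (SAP Section 7.9.4.1), so there the size of the estimate is the whole result.

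**Working it through.** The plan states no figure for this endpoint, so there is nothing to reproduce. The check applies the rule directly.

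**Inputs from the documents.** Weeks 1–11 have 7 days each. Week 12 runs from Day 78 to the last dose, usually Day 85, which makes 8 days (SAP Table 9.2-1). The baseline window starts 14 days before randomization.

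**Assumed for illustration.** Rescue use on 2 days of every week before and during treatment, hence 4 of 14 baseline days.

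**Formulas.** Literal value = 100 × d/D, with d = days of use in the week and D = days on treatment. Matched weekly value = 100 × d/7 (8 in Week 12). Shrink factor = D/7 (D/8 in Week 12).

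**Weekly level**
- Completer, literal: 2/85 = 2.4%. Matched weekly: 2/7 = 28.6%. Matched period: 24/85 = 28.2%.
- The 12 literal values sum to 12 × 2.353 = 28.2%; they should average to it.
- Shrink factor: 85/7 = 12.1, or 85/8 = 10.6 in Week 12.
- Patient stopping at Day 28: 2/28 = 7.1%, factor 28/7 = 4.
- Use on every day of a 7-day week scores at most 7/85 = 8.2%. In Week 1 a patient who follows protocol Section 7.7 takes no rescue medicine through the day after randomization, which leaves Days 3–7 and a maximum of 5/85 = 5.9%.
- If every patient completes, a true between-arm difference of 10 points in a 7-day week is reported as 10 × 7/85 = 0.8 points.

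**Change from baseline, use unchanged**
- Completer: 2.35 − 28.57 = −26.2 points. Matched weekly rule: 28.57 − 28.57 = 0.
- Stopping at Day 28: 7.14 − 28.57 = −21.4 points.
- If the pre-randomization part of Day 1 counts as a fifteenth day, baseline is 4/15 = 26.7%, and the two changes become −24.3 and −19.5.

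**RW Period.** The factor is 28/7 = 4 if days on treatment restart, and 112/7 = 16 if they accumulate over 16 weeks. The text does not say which.

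**Test statistic.** The documents give no use rates or dropout for this endpoint, so this part rests on assumptions. The simulation used 300 patients per arm and 200 repetitions. Mean use was 1/4.5 = 22.2% of days on placebo and 22.2 × 0.12/0.20 = 13.3% on linaclotide. Dropout was spread evenly over Days 1–84 and unrelated to use. Each week was analysed by a linear model with treatment and baseline, with 7 days per week throughout.

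| Dropout (placebo/linaclotide) | Week | Difference, matched | Difference, literal | t, matched | t, literal |
|---|---|---|---|---|---|
| 0/0 | 1 | −8.80 | −0.72 | −7.00 | −7.00 |
| 15%/20% | 1 | −8.73 | −0.79 | −6.91 | −3.50 |
| 15%/20% | 5 | −8.99 | −0.76 | −6.83 | −6.28 |
| 15%/20% | 12 | −8.73 | −0.72 | −6.29 | −6.29 |

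A repeat with the same dropout gave about −6.6 against −3.4 in Week 1, −6.3 against −5.8 in Week 5, and no difference in Week 12. With equal durations the literal rule only rescales the outcome, so t is unchanged. With dropout, early withdrawers have a small D and hence inflated early values, which adds noise.

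Without dropout, the mean Week 1 change moved from −0.1 to −20.4 points on placebo and from −8.8 to −21.0 on linaclotide: both arms move towards minus the baseline.

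**The case against.** The best defence is that the intent is plain. The sentence speaks of each week, so days on treatment could be read as days on treatment in that week, and a ceiling near 8% would be noticed on first output. The table specifications are in a separate document (SAP Section 1.0), so the slip may already be resolved there. This limits what can be claimed about the eventual report. It does not settle the text, because the SAP title points to the whole period instead, and that reading needs another numerator and another model.

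The endpoint is also one of many exploratory ones outside multiplicity control (protocol Section 10.4.6, SAP Section 7.9.3). That stands and limits the weight of the point.

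Four stronger readings are tempting but not supported.
- A reader might infer that everything shrinks 12-fold. The factor is D/7 for each patient, about 12 only for completers, and the change from baseline does not shrink; it moves towards minus the baseline.
- A reader might infer that the test is unaffected because only the scale changes. That holds only when durations are equal. Nor can a particular loss of power be claimed, because the documents give no dropout or use rates.
- A reader might infer that the plan prescribes an MMRM that cannot be fitted to one period value per patient. Protocol Section 10.4.7 alone suggests this, but SAP Section 7.9.3.1 limits the MMRM to endpoints at each week. Under the SAP, a period value is left without a clearly assigned model.
- A reader might infer a threat to the main results. The primary and secondary endpoints do not use this variable.

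**Conclusion.** The definition is wrong as written, identically in both documents. Weekly levels are too small by about D/7: 12.1 for a completer with last dose on Day 85, 10.6 in an 8-day Week 12, and 4 for a patient stopping at Day 28. Between-arm differences shrink by about the completer factor when most patients complete.

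Change from baseline combines two scales; the size of the spurious fall, −26.2 points in the example, depends on the assumed 4/14 baseline. The arithmetic on levels needs only the literal rule and SAP Table 9.2-1. The loss in the Week 1 test statistic is an illustration under assumed rates and dropout, from single-week models and not the full MMRM. It shows that treatment duration enters the score; it does not predict this trial's result.

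The consequence is confined to an exploratory endpoint and its descriptive RW counterpart, and depends on the rule being programmed literally. Alpha, sample size, and primary and secondary results are unaffected. It should be corrected before unblinding, so that the choice between a weekly and a period value cannot follow the data.

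**What to change.** Match numerator and denominator in SAP Section 7.9.3, and align title and model. Either of two versions works.

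- **(a) Weekly value.** 100 × days with use in the analysis week / days in that analysis week, using SAP Table 9.2-1. For withdrawals, SAP Section 9.2 already provides that "The affected Treatment Period or RW Period week shall be shortened". Title it by week and analyse it with the MMRM.
- **(b) Period value.** 100 × days with use in the period / days in that period. Keep the SAP title and name a model for one value per patient, for example the one already used for IBS-QOL in SAP Section 7.12.1: "ANCOVA model with fixed effect terms for treatment group and geographic region and the corresponding baseline IBS-QOL score as a covariate", with the baseline rescue percentage in place of the IBS-QOL score.

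Under either version, apply the same rule to the pretreatment window and say whether the pre-randomization part of Day 1 counts (14 or 15 days). Exclusion criterion 19 bars use on that day before randomization, so counting it adds only a day without use. Apply the rule to the RW Period with that period's own days. How missed diary days are treated (SAP Section 9.4.2: "analyses will assume that no rescue medicine use or BMs occurred during these gaps") is a separate matter that this change does not touch.

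The cost is one or two sentences in SAP Section 7.9.3, a matching line in Section 7.9.4, a model sentence in Section 7.9.3.1 if (b) is chosen, and an entry in Section 8.0 recording the difference from protocol Section 10.4.6. No new data are needed.
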